4.3.3 Exploratory Efficacy Endpoints

The exploratory efficacy endpoints include:

- Disability improvement response rate on the EDSS, T25FW, 9HPT-D, and 9HPT-ND at Weeks 12, 24, 36, and 52, and the EDSS + at Weeks 12, 24, and 36.
- Change from Baseline on the T25FW, 9HPT-D, 9HPT-ND at Weeks 12, 24, 36, and 52
- Disability progression response rate on the Expanded Disability Status Scale Plus (EDSS +) (T25FW, 9-Hole Peg test [9HPT, either hand], EDSS) and for each EDSS + component

- 12- and 24-week confirmed disability improvement response rate on the EDSS + and for each EDSS + component
- Change from Baseline on the Multiple Sclerosis Impact Scale (MSIS-29) total score at Weeks 12, 24, 36, and 52
- Change from Baseline on the Modified Fatigue Impact Scale (MFIS) total score at Weeks 12, 24, 36, and 52
- Change from Baseline on cognition battery at Weeks 12, 24, 36, and 52:
 - Total score of the Symbol Digit Modalities Test (SDMT) – Oral Version
 - Total score and T-score of the Brief Assessment of Cognition Verbal Memory - Immediate Recall – BAC App Version
 - Total score and T-score of the Brief Assessment of Cognition Tower of London – BAC App Version
- Change from Baseline on the Low Contrast Visual Acuity (LCVA) assessments at Weeks 12, 24, 36, and 52
- Change from Baseline in select plasma biomarkers for monitoring target binding, neuroprotection and/or neurorestoration at Weeks 12, 24, 36, and 52
- Change from Baseline on the MS Individualized Outcome Assessment (MSIOA) scale overall symptom score and most bothersome symptom score at Weeks 24, and 52
- Change from Week 0 in average daily step count and other activity measures (as described in Section 9.4.3) via home actigraphy with wearable biosensor initiated at Weeks 24, 36, and 52
- Summary of variables from brain MRI at Baseline, Weeks 24 and 52
 - Presence of active T1 Gadolinium (GAD)-enhancing lesions
 - Presence of active new and enlarging T2 hyperintense lesions
 - Cumulative number of total T1 GAD-enhancing, lesions
 - Cumulative number of total T2 hyperintense lesions
 - Cumulative number of post-baseline T1 GAD-enhancing lesions
 - Cumulative number of post-baseline new and enlarging T2 lesions
 - Number of T1 GAD-enhancing lesions at each visit
 - Change from Baseline in total volumes of T1 GAD-enhancing, lesions

- Change from Baseline in total volume of T2 hyperintense lesions

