- Change from Baseline in whole brain, gray matter (GM), thalamus, white matter (WM) and normal appearing white matter (NAWM) volumes
- Change from Baseline in regional magnetization transfer ratio (MTR) parameters for whole brain, and NAWM, and MTR for T2 lesions
- Change from baseline in lesion MTR for T1 (GAD)-enhancing lesions and delta MTR
- Change from Baseline in diffusion tensor imaging (DTI) parameters (fractional anisotropy and Apparent Diffusion Coefficient (ADC)) for whole brain, NAWM and T2 hyperintense lesions
- Summary of variables from cervical spinal MRI at Weeks 24 and 52
 - Change from Baseline in cervical spinal cord area, volume and number of lesions
 - Change from Baseline in regional MTR for cervical spinal cord lesions
 - Change from baseline in DTI parameters (fractional anisotropy and ADC) for cervical spinal cord

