9.4.11 MRI Parameters

The MRI parameters of interest and analyses are listed in Section [4.3.3](#).

The number and percentage of subjects with active lesions will be summarized for T1 GAD-enhancing lesions and T2 hyperintense lesions (separately). The difference in the proportion between elezanumab and placebo groups with the 95% confidence interval for the difference based on Wald confidence limits will be presented.

The cumulative number of total T1 GAD-enhancing lesions, cumulative number of total T2 hyperintense lesions, cumulative number of post-baseline T1 GAD-enhancing lesions, cumulative number of post-baseline new and enlarging T2-lesions, will be summarized with continuously and analyzed using an analysis of covariance (ANCOVA). The model for the analysis of the cumulative number of total lesions will include treatment, the stratification factors of diagnosis of MS (RRMS or rSPMS) and background MS immunotherapy (Yes or No). For the cumulative number of lesions during the treatment period, only subjects with Baseline, Week 24, and Week 52 MRIs will be included. For the cumulative number of lesions post-baseline, only subjects with Week 24 and Week 52 will be included.

The number of T1 GAD-enhancing lesions at each visit (Baseline, Week 24, Week 52) will be summarized categorically with the number and percent of subjects for the following categories: 0, 1, 2, 3, 4, 5, > 5.

The following endpoints will be analyzed using change or percent change from baseline using an ANCOVA model.

- Change from Baseline in total volumes of T1 GAD-enhancing lesions
- Change from Baseline in total volume of T2 hyperintense lesions
- Percent change from Baseline in whole brain, gray matter (GM), thalamus, white matter (WM) and normal appearing white matter (NAWM) volumes
- Change from Baseline in regional magnetization transfer ratio (MTR) parameters for whole brain, and NAWM, and MTR for T2 lesions

- Change from Baseline in diffusion tensor imaging (DTI) parameters (fractional anisotropy and Apparent Diffusion Coefficient (ADC)) for whole brain, NAWM and T2 hyperintense lesions
- Change from Baseline in cervical spinal cord area, volume and number of lesions
- Change from Baseline in regional MTR for cervical spinal cord lesions
- Change from baseline in DTI parameters (fractional anisotropy and ADC) for cervical spinal cord

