The model for the change from baseline analysis will include treatment, the stratification factors of diagnosis of MS (RRMS or rSPMS) and background MS immunotherapy (Yes or No), and the baseline value. For each treatment group, the number of subjects, mean, standard deviation, minimum, and maximum, will be presented, as well as the LS means and standard error, and the between group difference, standard error, and 95% confidence interval.

The change from baseline in lesion MTR for T1 GAD-enhancing lesions and delta MTR will be analyzed using an MMRM. The change from baseline will be calculated for each unique lesion within a treatment group. A dummy code will be created based on each subject-lesion to describe each unique lesion. The model will include the fixed effects of treatment, visit, the stratification factors of diagnosis of MS (RRMS or rSPMS) and background MS immunotherapy (Yes or No), and the treatment-by-visit interaction, with baseline MTR value as a covariate. The RANDOM statement will be used for each subject. The REPEATED statement will be used for visit with blocks in the covariance matrix identified by unique lesion nested within subject nested within treatment group. The unstructured covariance structure will be used to estimate the within subject variance-covariance. If the model fails to converge, the first order autoregressive (AR[1]) covariance structure will be substituted. If the model still fails to converge, the compound symmetry (CS) covariance structure will be substituted. Denominator degrees of freedom will be computed using the Kenward-Roger method.

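### The cumulative total T2 lesion count includes the pre-dose scan, has no stated counting rule and is not adjusted for baseline count, so its treatment contrast is likely to be very imprecise

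*SAP*

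**What the plan says.** SAP 4.3.3 introduces the brain imaging endpoints as "Summary of variables from brain MRI at Baseline, Weeks 24 and 52". One of them is "Cumulative number of total T2 hyperintense lesions", given by name only. A separate entry, "Cumulative number of post-baseline new and enlarging T2 lesions", covers lesion activity on study, so the total is not confined to new activity.

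SAP 9.4.11 sets the scan requirements: "For the cumulative number of lesions during the treatment period, only subjects with Baseline, Week 24, and Week 52 MRIs will be included". For the other family of counts it says: "For the cumulative number of lesions post-baseline, only subjects with Week 24 and Week 52 will be included". The pre-dose scan is therefore part of the total and not of the post-baseline count.

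The cumulative counts are to be analysed by ANCOVA. The terms are listed as follows: "The model for the analysis of the cumulative number of total lesions will include treatment, the stratification factors of diagnosis of MS", and then background immunotherapy. That sentence lists no baseline lesion count. Later in the same section, the model for the change-from-baseline imaging endpoints has the same factors and does add it: "background MS immunotherapy (Yes or No), and the baseline value".

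For the cervical cord, SAP 4.3.3 uses a different form: "Change from Baseline in cervical spinal cord area, volume and number of lesions".

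**The concern.** Two things are left open or omitted.

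- **Counting rule.** T2 lesions generally remain visible from scan to scan. The SAP does not say whether a lesion seen on three scans adds one to the cumulative total or three. Two programmers could follow the text and report figures about threefold apart.
- **Baseline burden.** Under either rule the outcome contains the lesions that each subject brought into the trial, which treatment cannot prevent. Subjects differ in that burden, and a model without the baseline count leaves the difference in the residual error.

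The line would still be tabulated with a treatment comparison. A null result could be read as no effect on lesion activity when the analysis had little chance of showing one.

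**Working it through.** The SAP states no figure for this endpoint, so there is nothing to reproduce. The documents give neither T2 counts nor new-lesion rates, so every count below is an assumption, shown over a range.

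**Set-up.** Let B be the baseline T2 count, and a and b the lesions first seen at Week 24 and Week 52, with none resolving.

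- Scan totals summed: B + (B + a) + (B + a + b) = 3B + 2a + b
- Each lesion counted once: B + a + b

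The pre-treatment share is 3B/(3B + 2a + b) or B/(B + a + b). For B = 20 and a = b = 1, these are 60/63 = 95% and 20/22 = 91%.

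| B | New per interval | Share, summed | Share, counted once |
|---|---|---|---|
| 5 | 1 | 83% | 71% |
| 5 | 3 | 62.5% | 45% |
| 10 | 1 | 91% | 83% |
| 20 | 1 | 95% | 91% |
| 50 | 0.25 | 99.5% | 99% |
| 50 | 1 | 98% | 96% |

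Over the full grid (B of 5 to 50; 0.25 to 3 new lesions per interval) the share runs from 45% to 99.5%. It falls below half only when lesions are counted once, B = 5 and there are 3 new lesions per interval.

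**Size of a treatment effect.** Suppose treatment halves new lesions, with B = 20 and a = b = 1.

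- Summed: falls by 1.5, and 1.5/63 = 2.4%
- Counted once: falls by 1, and 1/22 = 4.5%
- Post-baseline new lesions only: falls by 1 out of 2, or 50%

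**Precision without baseline adjustment.** Assume negative-binomial counts with variance m + m²/k, taking k = 1.5 for baseline and k = 0.5 for new lesions, independent of each other. Then Var(B) = 20 + 400/1.5 = 286.7, and Var(a) = Var(b) = 1 + 1/0.5 = 3.

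- Summed: variance 9 × 286.7 + 4 × 3 + 3 = 2595, SD 50.9; standardized difference 1.5/50.9 = 0.03
- Counted once: variance 286.7 + 3 + 3 = 292.7, SD 17.1; standardized difference 1/17.1 = 0.06
- New lesions only: variance 6, SD 2.45; standardized difference 1/2.45 = 0.41

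Baseline count explains 2580/2595 = 0.99 of the variance of the summed outcome and 286.7/292.7 = 0.98 of the counted-once outcome. Over the grid, simulation gave 0.65 to 1.00 and 0.34 to 1.00. At the most favourable corner (B = 5, 3 new per interval) the standardized differences were 0.26 summed, 0.38 counted once and 0.47 for new lesions only, so the loss there is much smaller.

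**With the baseline count as covariate.** In the central case the residual variance is 4 × 3 + 3 = 15 (summed) or 6 (counted once). The standardized differences become 1.5/3.87 = 0.39 and 1/2.45 = 0.41. Almost all the loss therefore comes from the unadjusted baseline burden. The unequal weighting of Week 24 and Week 52 lesions in the summed form costs little.

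**Power check.** A simulation assumed 45 complete cases per arm, 2.0 against 0.6 new lesions, two-sided 0.05 and a baseline mean of 20. Power was about 6% for the unadjusted sum and 87% for new lesions. Adjusting the sum for baseline restored 86%. A second run with different dispersion gave 6% for the unadjusted sum, 8% counted once, 97% to 98% for new lesions, and 96% to 97% for the adjusted sum.

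**The case against.** The strongest objection concerns what the text establishes. A reader might infer that the SAP sums the three scans, so that a persisting lesion is counted three times and the reported mean is about three times the true burden. The documents do not support that as fact. The three-scan sentence in SAP 9.4.11 says who enters the analysis, not how lesions are added. Baseline lesions plus later new ones, each counted once, fits the wording as well. SAP 11.1 also mentions a statistical programming plan that further defines programming, and a counting rule could be there. This part of the objection stands, so summation is treated here as one possible reading.

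Second, lesion activity is covered elsewhere. The SAP plans the presence of active new and enlarging T2 lesions, their post-baseline cumulative number, and change in T2 volume with the baseline value in the model. That also stands and limits the consequence.

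Third, the counts are assumed, and a large cut in new lesions may not fit this trial. Protocol 2.1 describes a mechanism distinct from anti-inflammatory drugs, and Protocol 4.2 selects subjects at reduced relapse risk. That makes the power figures illustrative. It does not rescue the endpoint, because fewer new lesions mean a larger pre-treatment share.

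Lastly, calling the model an ANCOVA may hint that a baseline covariate was intended. If so, the list of terms should include it.

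**Conclusion.** The point holds in this form: the endpoint includes the pre-dose scan, its counting rule is not stated in the SAP, and the listed model has no baseline lesion count. Under either counting rule the outcome is likely to be dominated by pre-treatment lesions. The treatment contrast is unbiased because of randomization, but in the central assumed case it is so imprecise as to be nearly uninformative.

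This rests on assumed lesion counts, no lesion resolution, and new-lesion counts unrelated to baseline count. With few baseline lesions and many new ones the problem shrinks. Triple counting is not established. Severity is low: this is one exploratory line in a Phase 2a study, and no primary or secondary conclusion uses it.

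**What to change.** In SAP 4.3.3 and 9.4.11, replace the endpoint with change from Baseline in the number of T2 hyperintense lesions at Weeks 24 and 52. The cervical cord endpoint already takes this form. Analyse it with the ANCOVA that SAP 9.4.11 gives for change-from-baseline imaging endpoints, which includes the baseline value.

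If the cumulative total is kept, state in SAP 9.4.11 that each lesion is counted once and add the baseline T2 count as a covariate.

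The cost is SAP wording and one table. It assumes that T2 counts for each scan are available from the image reads; the SAP lists a count at each visit only for T1 gadolinium-enhancing lesions, so this should be confirmed. The replacement overlaps with the planned post-baseline new and enlarging T2 count: if no lesion resolves, the change at Week 52 is a + b, the number of new lesions.

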4.3.4 Safety Endpoints

Safety variables include adverse events (AEs), serious adverse events (SAEs), adverse events of special interest (AESI), vital sign measurements (including pre and post-infusion blood pressure), MS relapses, electrocardiogram (ECG) variables, Columbia-Suicide Severity Rating Scale (C-SSRS) assessments, and clinical laboratory testing (hematology, chemistry, and urinalysis) as measures of safety and tolerability for the entire study duration.

4.4 Sample Size Justification

Approximately 165 subjects will be equally randomized 1:1:1 to each treatment group (approximately 55 subjects in each treatment, with at least 20 rSPMS subjects and approximately 35 RRMS subjects). There is limited prior data to estimate the magnitude of effect and variance. This sample size will have approximately 80% power to detect an

effect size (ES) of 0.43 with significance level of 0.1 and overall dropout rate of approximately 10%, using a 1-sided t-test.

4.5 Interim Analysis

An interim futility analysis was planned to assess study and/or dose futility when approximately 40% of planned subjects completed the Week 24 assessment. However, due to the pattern of enrollment and missed infusions and efficacy data collection as a result of the COVID-19 pandemic, the interim futility analysis was eliminated.

4.6 Multiplicity Testing Procedures for Type-I Error Control

No multiplicity adjustment will be performed for this Phase 2a proof of concept study.

4.7 Missing Data Imputation

For continuous efficacy variables, data will be summarized using a mixed-effect model for repeated measures (MMRM) model unless otherwise specified. Missing data will not be imputed before applying an MMRM model. The MMRM model relies on a missing at random (MAR) assumption.

For sensitivity analyses of the primary and secondary efficacy variables, missing values will be imputed using multiple imputation (MI) and categorized as responder/non-responder after imputation. The MI model also relies on a MAR assumption.

Justification for the MAR Assumption:

The COVID-19 pandemic is interfering with the conduct of many ongoing trials, with potential impact on treatment duration and the collection, analysis and the interpretation of clinical trial data. Some protocol-specified visits in this clinical trial may be impacted due to COVID-19 infection or logistical restrictions during the pandemic. For example, some scheduled visits may be missed due to self-quarantine or local government restrictions on travel; some visits may also be delayed or canceled due to healthcare resource constraints during the pandemic. These missed visits will be recorded in the

database. The probability of having missed visits and missing data due to COVID-19 infection or logistical restrictions related to the COVID-19 pandemic can be reasonably assumed to be unrelated to the unobserved values conditional on the observed data.

Therefore, for the purpose of statistical analysis, it is reasonable to assume that these missing data are missing at random (MAR) and the statistical models that require MAR assumption are appropriate. In some cases, sensitivity analyses may be performed to assess the impact of missing data and the robustness of the conclusion.

Where noted, summaries as observed will not impute values for missing evaluations, and thus a subject who does not have an evaluation on a scheduled visit will be excluded from the as observed for that visit.

Safety variables will be summarized as observed.

5.0 Analysis Sets and Important Subgroups

5.1 Analysis Sets

The Modified Intent-to-Treat (mITT) Analysis Set includes all randomized subjects who receive at least 1 dose of study drug. Subjects will be grouped according to treatment as randomized. The mITT analysis set will be used for all demographic and efficacy analyses, unless otherwise noted.

MS expert(s) will confirm which subjects experienced a clinical relapse(s) through adjudication of study data, including the MS-relapse questionnaire. The Relapse-Free (RF) Analysis Set includes all subjects in the mITT analysis set without any MS-related relapse during the Treatment Period (from Week 0 to Week 52). Subjects will be grouped according to treatment as randomized.

Due to the COVID-19 pandemic, a subset of the study population missed one or more study drug infusions. For the purposes of conducting a sensitivity analysis of the primary and secondary endpoints, the Minimal Missed Infusion Analysis (MMIA) Set includes all randomized subjects who received at least 6 infusions total and missed no consecutive

infusions prior to the subject's final dose. Subjects will be grouped according to treatment as randomized.

The Safety Analysis Set consists of all subjects who received at least 1 dose of study drug. Subjects will be grouped according to treatment received regardless of randomization.

If a subject was randomized to treatment X, but received treatment Y during the entire study, this subject will be included in the Y treatment group for analysis purposes. If a subject receives both treatments but one > 50% of the time, the subject will be included in that treatment group. If a subject receives both treatments an equal percentage of the time, the subject will be analyzed in the treatment group to which they were randomized.

5.2 Subgroups

The primary efficacy and secondary variables will also be analyzed by the following subgroups to assess the consistency of the treatment effect:

- Sex (male, female)
- Age (\leq 40, $>$ 40)
- EDSS baseline (\leq Median, $>$ Median)
- Diagnosis of MS form (relapsing remitting MS [RRMS] vs. relapsing secondary-progressive MS [rSPMS]) if at least 20% of subjects are in each stratum
- Presence of background MS immunotherapy (Yes vs. No) if at least 20% of subjects are in each stratum

6.0 Subject Disposition

A summary of subject accountability will be provided where the number of subjects in each of the following categories will be summarized for each treatment group and overall, for the whole study and by investigator based on all randomized subjects:

- Subjects enrolled (randomized) in the study;

- Subjects who took at least one dose of study drug;
- Subjects who completed protocol-specified treatment;
- Subjects who prematurely discontinued study drug
- Subjects who discontinued the study
- Subjects in each of the following analysis sets: Safety Analysis Set, mITT analysis set, RF analysis set, MMIA set

The reasons for study drug discontinuation and study discontinuation will be summarized with the number and percentage of subjects for all reasons and the primary reason for the mITT analysis set by treatment group.

A summary of subject disposition will include the number randomized, number that never received study drug, number that received study drug other than randomized, and the number in each of the analysis sets noted in Section 5.1 for all subjects randomized by treatment group.

7.0 Extent of Exposure and Compliance

For the mITT analysis set, extent of exposure will be summarized for each treatment group. Extent of exposure will be summarized as duration of treatment and number of infusions. Duration of treatment is defined for each subject as last dose date minus first dose date + 28. A gap in treatment due to missed infusions will not be considered in the calculation of study duration. Duration of treatment will be summarized using the number of subjects treated, mean, standard deviation, median, minimum and maximum. In addition, the number and percentage of subjects in each unique treatment duration interval (28, 29 to 56, 57 to 84, 85 to 112, 113 to 140, 141 to 168, 169 to 196, 197 to 224, 225 to 252, 253 to 280, 281 to 308, 309 to 336, 337 to 364, > 364) will be summarized.

The number and percentage of subjects for each number of infusions from 1 to 13 will be summarized.

The number and percentage of completed and missed infusions by visit will be summarized at each visit from Day 1 to Week 48. The reason for missed infusions will be summarized at each visit.

The number of missed infusions by subject prior to the subject's last dose or premature discontinuation from study drug will be summarized by treatment group.

Because the treatment is administered by the site, compliance will not be summarized.

